11.1.2 Clinical Endpoints

Evaluable patients are defined as eligible participants who received at least one dose of the protocol treatment. Eligible participants who did not receive any protocol treatment will be considered in-evaluable, replaced, and excluded from all analyses.

Endpoint	Patients	Definition
Progression-Free Survival (PFS)*	Evaluable patients	Defined as the time from the first dose of study treatment to the first observation of disease relapse/progression or death from any cause, whichever occurs first. For patients who are alive and have not had disease relapse/progression at the last follow-up, it is censored at the time of last follow-up. If a patient receives non-protocol anti-HL treatment prior to disease relapse/progression, the patient will be censored at the time of non-protocol anti-HL treatment.

Endpoint	Patients	Definition
Overall Survival (OS)	Evaluable patients	Defined as the time from the first dose of study treatment to death from any cause. For patients alive at the last follow-up, it is censored at the time of last follow-up.
Cumulative Incidence of Non-Relapse Mortality (NRM)*	Evaluable patients	Defined as the time from the first dose of study treatment to non-disease related death. Disease relapse or progression is considered a competing risk. For surviving patients without disease relapse/progression at the last follow-up, it is censored at the time of last follow-up. If a patient receives non-protocol anti-HL treatment prior to disease relapse/progression, the patient will be censored at the time of non-protocol anti-HL treatment.
Cumulative Incidence of Relapse/Progression*	Evaluable patients	Defined as the time from the first dose of study treatment to disease relapse/progression. Death without relapse/progression is considered a competing risk. For surviving patients without relapse/progression at the last follow-up, it is censored at the time of last follow-up. If a patient receives non-protocol anti-HL treatment prior to disease relapse/progression, the patient will be censored at the time of non-protocol anti-HL treatment.
Overall response rate (ORR)	Evaluable patients with measurable disease post-ASCT	Proportion of patients achieving CR or PR [53]

* **For patients who meet PD per Lugano Classification and also meet IR per LYRIC criteria (Appendix H) [1]:** In the analysis, patients with PD per Lugano classification and IR per LYRIC criteria who continue study treatment beyond progression per Lugano classification and have confirmation of subsequent PD per LYRIC criteria will be counted as PD at the initial time point of progression per Lugano classification; patients with PD per Lugano classification and IR per LYRIC criteria who continue study treatment beyond progression per Lugano classification and do not have confirmation of subsequent PD per LYRIC criteria, with subsequent SD, PR, or CR per Lugano classification, will NOT be counted as PD at the initial time point of progression per Lugano classification. Patients with PD per Lugano classification and IR per LYRIC criteria who did NOT continue study treatment beyond progression per Lugano classification will be considered PD at the initial timepoint of progression per Lugano classification.

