5.9 Supportive care, Prohibited and Concomitant Medications/ Therapies

Participants must be instructed not to take any additional medications (including over-the-counter products) during the trial without prior consultation with the investigator.

5.9.1 *Prohibited medications/ therapies*

The following medications/ therapies are **prohibited** from Day 1 of protocol therapy until end of protocol therapy (last day of study agent or decision to end study agent(s) whichever occurs later):

- Co-medication that may interfere with study results; e.g. immuno-suppressive agents other than corticosteroids used for treatment of an IrAE are prohibited during the treatment period, unless discussed with the Study PI and felt to be of low clinical risk to the participant.
- Live attenuated vaccines
- Herbal and natural remedies

The following medications/therapies are prohibited any time after ASCT, active protocol treatment, or follow-up. If the patient receives one of these therapies in the absence of disease progression, the patient will be censored at the time of initiation.

- Other investigational therapy
- Concurrent anti-cancer therapy: chemotherapy, biological response modifiers, hormone therapy, surgery, palliative radiation therapy, or immunotherapy).

5.9.2 *Supportive care and permitted medications/ therapies*

With the exception of prohibited therapies (see [Section 5.9.1](#)), participants should receive prophylactic or supportive care as clinically indicated per institutional policies and suspected immune-related AEs (irAE) guidelines stated below.

Blood products

- *Platelet and/or red blood cell supportive growth factors or transfusions*
 - Permitted when applicable
- *Colony stimulating factors (CSFs)*
 - Permitted for treatment of neutropenia per institutional practice.

Corticosteroids

- *Topical, ocular, intra-articular, intranasal, and inhalational corticosteroids (with minimal systemic absorption)*
 - Permitted
- *Systemic corticosteroids*
 - Physiologic replacement doses permitted even if > 10 mg/day prednisone or equivalent.
- *Brief course of corticosteroids (< 3 weeks)*
 - Permitted for prophylaxis (e.g. contrast dye allergy)
 - Permitted for treatment of non-autoimmune conditions (e.g. delayed-type hypersensitivity reaction caused by contact allergen)

Strong CYP3A4/5 inhibitors

Closely monitor for AEs when administered concomitantly with brentuximab vedotin.

Required prophylaxis

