12.3 Statistical Analysis Plan

12.3.1 Power Estimation

The primary endpoint is 18-month PFS, as defined in [Section 11.0](#). Eligible participants who received at least one dose of the protocol treatment will be evaluable for the primary endpoint; eligible participants who did not receive any protocol treatment will be considered in-evaluable and excluded from all analyses.

Based on the AETHERA trial, the 18-month PFS rate in patients with relapsed/refractory HL who undergo ASCT followed by BV consolidation is approximately 65% (from the independent assessment data) [32]. We hypothesize that adding nivolumab to BV consolidation after ASCT will improve the 18-month PFS rate to 80%. A sample size of 59 evaluable patients will provide approximately 81% power for detecting the

increase in 18-month PFS from the baseline of 65% to 80% in this study at 1-sided type I error of 0.05. The power estimation is based on the exact binomial test. Operationally, the study treatment will be considered promising if at least 45 of the 59 evaluable participants are alive and progression-free at 18 months after the first dose of study treatment. The probability of observing at least 45 surviving and progression-free participants out of a total 59 participants, assuming different PFS rates, is shown in [Table 12.3.1](#).

Table 12.3.1 The probability of declaring the trial a success assuming different PFS rates

	True 18-month PFS rate			
	65%	70%	75%	80%
The probability of observing at least 45 participants (out of 59 total) being alive and progression-free at 18-month	0.044	0.18	0.48	0.81

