12.3.2 Analysis Plans

Patient demographics and baseline disease characteristics, including age, gender, medical history, and prior therapy, will be summarized using descriptive statistics. For continuous variables, descriptive statistics such as number, mean, standard deviation, standard error, median (range) etc. will be provided. For categorical variables, patient counts and percentages will be provided.

For all analyses, only eligible participants who received at least one dose of protocol treatment will be considered evaluable and included in the analyses. Eligible participants who did not receive any protocol treatment will be considered in-evaluable and excluded from all analyses.

PFS will be estimated using the product-limit method of Kaplan and Meier along with the Greenwood estimator of standard error. When there is no censoring in PFS prior to 18 months after the first dose of study treatment, the observed 18-month PFS will be compared to the baseline of 65% by one-sided exact test of binomial proportion. In case of censoring in PFS prior to 18 months after the first dose of study treatment (which are expected to be rare), the Kaplan-Meier estimate for 18-month PFS along with the Greenwood standard error estimator will be used for the testing of null hypothesis at 65%.

OS will be estimated using the product-limit method of Kaplan and Meier along with the Greenwood estimator of standard error. Cumulative incidence of relapse/progression and cumulative incidence of non-relapse mortality, as well as their confidence intervals will be estimated using competing risk methodology, treating the other event as a competing risk. Overall response rate will be estimated by the proportion of patients achieving either CR or PR among participants with measurable disease after ASCT, along with the exact binomial confidence interval.

Observed toxicities will be summarized by type (organ affected or laboratory determination such as absolute neutrophil count), severity (by NCI CTCAE v4.0 and nadir or maximum values for lab measures), date of onset, duration, reversibility, and attribution.

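### Patients who start other anti-HL therapy before progression are censored, which changes the primary test, yet 12.3.1 states the 45-of-59 rule without a condition and no analysis checks the effect of the censoring

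*Combined protocol and SAP*

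**What the plan says.** **Endpoint definition (Section 11.1.2).** PFS runs from first dose to relapse, progression or death, with this exception: "If a patient receives non-protocol anti-HL treatment prior to disease relapse/progression, the patient will be censored at the time of non-protocol anti-HL treatment". Section 5.9.1 says the same of investigational and other anti-cancer therapy: "If the patient receives one of these therapies in the absence of disease progression, the patient will be censored at the time of initiation".

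**Success rule (Section 12.3.1, repeated in the synopsis).** "Operationally, the study treatment will be considered promising if at least 45 of the 59 evaluable participants are alive and progression-free at 18 months". No condition about censoring is attached. The design figures rest on this fixed denominator: "The power estimation is based on the exact binomial test".

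**Primary test (Section 12.3.2).** If nobody is censored before 18 months, a one-sided exact binomial test against 65% is used. Otherwise, "the Kaplan-Meier estimate for 18-month PFS along with the Greenwood standard error estimator will be used for the testing of null hypothesis at 65" (per cent). Early censoring is expected to be rare, but no number is given. The scale of the Kaplan-Meier test is not stated.

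The documents do not say how a patient censored for other therapy enters the count of 45. They plan no sensitivity analysis of this censoring.

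**The concern.** Call a patient who starts non-protocol anti-HL therapy before documented progression a switcher. There are two separate problems.

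First, one switcher moves the trial from the exact test to a different test, while 12.3.1 still reads as if the count decides. The two can give opposite answers on the same data, and a reader of 12.3.1 alone would not know which one holds.

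Second, Kaplan-Meier censoring assumes that a switcher had the same later risk as patients who stayed. If therapy tends to be started because relapse is suspected, that assumption fails in the regimen's favour. The setting gives some reason for care. The trial is open-label, response is assessed by the investigator from site radiology reads (Section 11.1.1), and scheduled active follow-up ends at new anticancer therapy (Section 10.0, note h). With one arm and a fixed 65% null, no control group shares any such bias.

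**Working it through.** **1. Reproduce the design.** Inputs from Section 12.3.1: n = 59, null 65%, alternative 80%, one-sided 0.05, success at 45 or more. Exact binomial tails P(X ≥ 45):

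| True 18-month PFS | Computed | Table 12.3.1 |
|---|---|---|
| 65% | 0.0436 | 0.044 |
| 70% | 0.1825 | 0.18 |
| 75% | 0.4801 | 0.48 |
| 80% | 0.8124 | 0.81 |

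The plan's figures are right. For a cut-off of 44, P(X ≥ 44 | 65%) = 0.0775.

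**2. Effect of changing the test, with complete data.** Without censoring, the Kaplan-Meier estimate is the simple proportion S, and the Greenwood sum is G = 1/(number left) − 1/59. The plain Wald statistic is z = (S − 0.65)/(S√G). The log-log statistic is z = [ln(−ln 0.65) − ln(−ln S)] / [√G/(−ln S)].

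- 44/59: S = 0.7458, SE = 0.0567. Wald z = 1.69, p = 0.0456. Log-log p = 0.069.
- 45/59: S = 0.7627, SE = 0.0554. Wald p = 0.021. Log-log z = 1.73, p = 0.042.

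The plain Wald test would therefore reject at 44, where the exact p is 0.0775. The log-log test keeps the cut-off at 45.

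**3. One switcher.** Assume 14 events spread evenly over months 1.5 to 17 and one patient censored at month 6. Four events precede the censoring and ten follow it.

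- Known progression-free at 18 months: 59 − 14 − 1 = 44. This is below 45, and the exact p is 0.0775.
- S = (55/59) × (44/54) = 0.7596.
- G = (1/55 − 1/59) + (1/44 − 1/54) = 0.00544, so SE = 0.7596 × √0.00544 = 0.0560.
- Wald z = (0.7596 − 0.65)/0.0560 = 1.96, p = 0.025.
- Log-log z = 1.67, p = 0.047.

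The Kaplan-Meier test passes on both scales. The count fails if the switcher is not counted as progression-free.

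**4. The other way of counting.** If switchers count as progression-free, the conflict can run in reverse. With 14 events and 5 patients censored at month 3, the count is 40 + 5 = 45 and passes. Kaplan-Meier PFS is 74.3% with Wald p = 0.058, and fails.

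**5. Type I error under assumed switching.** The documents give no rate, so 2%, 3% and 5% of patients (about 1 to 3 of 59) are assumptions. Failure times are exponential with 65% failure-free at 18 months, and switching counts as failure in that 65%. The plan's rule is applied: the exact test if nobody is censored, Kaplan-Meier otherwise.

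| Switching | Plain Wald | Log-log |
|---|---|---|
| 2%, every switcher a true failure | about 9% | about 7% |
| 3%, every switcher a true failure | about 11% | about 9% |
| 5%, every switcher a true failure | about 18% | about 13% |
| 2-5%, non-informative censoring | about 5-6% | about 4% |

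If switchers are counted as failures under the 45-of-59 rule, the error stays near 4.4%.

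**The case against.** **The plan already orders its tests.** Section 12.3.2 can fairly be read as one conditional primary test, with 45 of 59 as its cut-off when nobody is censored. The count sits under Power Estimation. A reader might infer that the plan contradicts itself, but the text does not go that far. What stands is that 12.3.1 and the synopsis omit the condition.

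**The count rule does not make a switcher a failure.** A reader might assume that it does. Section 12.3.1 is silent, and a patient who switched but is alive without progression at 18 months literally fits its wording.

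**Nothing in the documents shows that switchers are failing.** Early censoring is expected to be rare, these therapies are prohibited during treatment and follow-up, and scans are scheduled. Lugano progression is already an event for a patient with indeterminate response who stops study treatment (11.1.2, footnote). Only switches before any Lugano progression remain. This limits the likely size. It does not rule the bias out, because one case is enough to change the test.

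**Some examples depend on the scale.** With 14 events and three switchers at month 6, 42 of 59 are known progression-free. Wald p is 0.036, but log-log p is 0.060 when events are spread evenly, so on that scale the test agrees with the count. The one-switcher case above does not depend on this choice.

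**Counting switching as failure changes the endpoint.** The 65% comes from the AETHERA independent assessment, and the documents do not say how that trial handled new therapy. This is a good reason not to let the composite decide success. It is not a reason to leave it unreported.

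**Conclusion.** The point holds in limited form. The unconditional 45-of-59 statement and the conditional test in 12.3.2 can disagree after a single switcher, and the plan states neither how that patient is counted nor the test scale. Pre-specifying the censoring is a defensible choice. Leaving it without any check is the weakness.

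The direction of bias depends on switching tending to precede progression, which is a judgement and not a finding in the documents. A reader might take 18% as the trial's false-positive rate. That figure needs 5% switching, every switcher a true failure, the plain Wald scale, and a null that counts switching as failure, which is not the plan's PFS definition. Across the assumptions tried, the range runs from about 4% (non-informative, log-log) to about 18%. The change should be made, but the point does not invalidate the design.

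**What to change.** **Section 12.3.1 and synopsis.** State that 45 of 59 is the success cut-off only when nobody is censored before 18 months, and that the test in 12.3.2 decides otherwise.

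**Section 12.3.2, test scale.** Specify the log-log scale for the Kaplan-Meier test. This keeps the cut-off at 45 with complete data. It does not remove bias from informative censoring.

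**Section 12.3.2, sensitivity analysis.** Add a pre-specified analysis that counts the start of non-protocol anti-HL therapy before 18 months as failure and applies the exact 45-of-59 rule. Report it beside the primary result, with the number of patients censored for this reason. Do not make the promising label conditional on it, because that would in effect replace the primary endpoint.

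**Cost.** A few sentences and one more analysis. The therapy start dates are already needed to apply the censoring rule. The sensitivity result may look less favourable, and the 65% null may not match the composite definition. The report should say so.

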11.1.3 Toxicity

Toxicity and adverse events will be recorded using the NCI CTCAE v 4.0. All toxicities/AEs will be recorded from the initiation of protocol therapy through the follow-up period. The highest grade for any toxicity plus Grade 3 or 4 event for the same toxicity (if not the highest grade) will be reported during each cycle and during the safety follow-up period.

Eligible participants who did not receive any protocol treatment will be considered in-evaluable, replaced, and excluded from all analyses on toxicity.

12.0 STATISTICAL CONSIDERATIONS

12.1 Study Design

This is a single-arm, open-label Phase 2 study of nivolumab plus BV consolidation following ASCT in patients with relapsed/ refractory HL who have undergone ASCT. Participants will receive protocol treatment consisting of 21-day cycles, for up to 8 cycles. The primary endpoint is 18-month progression-free survival. Secondary endpoints include overall survival, cumulative incidence of relapse/progression, cumulative incidence of non-relapse mortality, overall response rate, and toxicity. The target sample size is 59 eligible participants who received at least one dose of the protocol treatment. Eligible participants who did not receive any protocol treatment will be considered in-evaluable and replaced. The total study accrual may be increased slightly beyond 59 patients in order to achieve 59 evaluable participants with at least one dose. To account for up to 10% inevaluable enrollments, the maximum study accrual is set to be 65 participants. The projected study accrual duration is 24 months at the estimated accrual rate of 2-3 patients per month. With a planned follow-up until 18 months from the first dose of study treatment for the last accrued patient, the projected total study duration for accrual and follow-up is approximately 42 months.

12.2 Sample Size Accrual Rate

The target sample size is 59 participants with at least one dose of the protocol treatment, with the study total accrual potentially slightly larger to accommodate some eligible participants who did not receive any protocol treatment due to various reasons. City of Hope performs approximately 20-30 ASCT in patients with HL each year. [Table 12.2](#) below describes the number of patients with HL evaluated at COH each year, as well as the number of ASCT for HL performed between 2011 and 2015. Based on this estimate, we expect to accrue 15-20 patients per year at COH. This will be a multicenter study with 6 total sites. We expect a total accrual of 2-3 patients per month across all sites. Therefore, accrual is expected to be completed in 24 months. With a planned follow-up until 18 months from the first dose of study treatment for the last accrued patient, the total anticipated study duration will be approximately 42 months.

Table 12.2 City of Hope Patient Availability

Disease Site	2011	2012	2013	2014	2015
Hodgkin Lymphoma (HL)	388	392	361	425	394
HL patients undergoing ASCT	21	33	22	33	30

12.3 Statistical Analysis Plan

12.3.1 Power Estimation

The primary endpoint is 18-month PFS, as defined in [Section 11.0](#). Eligible participants who received at least one dose of the protocol treatment will be evaluable for the primary endpoint; eligible participants who did not receive any protocol treatment will be considered in-evaluable and excluded from all analyses.

Based on the AETHERA trial, the 18-month PFS rate in patients with relapsed/refractory HL who undergo ASCT followed by BV consolidation is approximately 65% (from the independent assessment data) [32]. We hypothesize that adding nivolumab to BV consolidation after ASCT will improve the 18-month PFS rate to 80%. A sample size of 59 evaluable patients will provide approximately 81% power for detecting the

increase in 18-month PFS from the baseline of 65% to 80% in this study at 1-sided type I error of 0.05. The power estimation is based on the exact binomial test. Operationally, the study treatment will be considered promising if at least 45 of the 59 evaluable participants are alive and progression-free at 18 months after the first dose of study treatment. The probability of observing at least 45 surviving and progression-free participants out of a total 59 participants, assuming different PFS rates, is shown in [Table 12.3.1](#).

Table 12.3.1 The probability of declaring the trial a success assuming different PFS rates

	True 18-month PFS rate			
	65%	70%	75%	80%
The probability of observing at least 45 participants (out of 59 total) being alive and progression-free at 18-month	0.044	0.18	0.48	0.81

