- **For patients who meet PD per Lugano Classification and also meet IR per LYRIC criteria (Appendix H)** **[1]:** In the analysis, patients with PD per Lugano classification and IR per LYRIC criteria who continue study treatment beyond progression per Lugano classification and have confirmation of subsequent PD per LYRIC criteria will be counted as PD at the initial time point of progression per Lugano classification; patients with PD per Lugano classification and IR per LYRIC criteria who continue study treatment beyond progression per Lugano classification and do not have confirmation of subsequent PD per LYRIC criteria, with subsequent SD, PR, or CR per Lugano classification, will NOT be counted as PD at the initial time point of progression per Lugano classification. Patients with PD per Lugano classification and IR per LYRIC criteria who did NOT continue study treatment beyond progression per Lugano classification will be considered PD at the initial time point of progression per Lugano classification.
- Toxicity and adverse events will be recorded using the NCI CTCAE v 4.0. All toxicities/AEs will be recorded from the initiation of protocol therapy through the follow-up period.

Statistical Considerations:

Based on the AETHERA trial, the 18-month PFS rate in patients with relapsed/refractory HL who undergo ASCT followed by BV consolidation is approximately 65% (from the independent assessment data). We hypothesize that adding nivolumab to BV consolidation after ASCT will improve the 18-month PFS rate to 80%. A sample size of 59 evaluable patients will provide approximately 81% power for detecting the increase in 18-month PFS from the baseline of 65% to 80% in this study at 1-sided type I error of 0.05. The power estimation is based on the exact binomial test. Operationally, the study treatment will be considered promising if at least 45 of the 59 evaluable participants are alive and progression-free at 18 months after the first dose of study treatment. The

probability of observing at least 45 surviving and progression-free participants out of a total 59 participants, assuming different PFS rates, is shown in below:

	True 18-month PFS rate			
	65%	70%	75%	80%
The probability of observing at least 45 participants (out of 59 total) being alive and progression-free at 18-months	0.044	0.18	0.48	0.81

To achieve 59 evaluable participants, the maximum study accrual is set to be 65, accounting for up to 10% inevaluable enrollments.

Toxicity Monitoring

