HL post ASCT and risk factors at baseline included refractory to frontline therapy (60%), relapsed < 12 months (33%), and extranodal disease at time of pre- ASCT relapse (33%). The median PFS per IRF for patients randomized to receive brentuximab vedotin was 42.9 months [95% CI (30.4, 42.9)] (range, 0.03+ to 42.94) compared with 24.1 months [95% CI (11.5, -)] (range, 0.03+ to 42.35+) for patients who received placebo. The difference between the 2 arms was statistically significant by stratified log-rank test ($P=0.001$). As assessed by Cox regression analysis, the stratified HR was 0.57 [95% CI (0.40, 0.81)]. The estimated 24-month PFS rate was 63% [95% CI (55%, 70%)] for patients in the brentuximab vedotin arm versus 51% [95% CI (43%, 59%)] for patients in the placebo arm.

An additional prespecified analysis per investigator assessment was performed that included clinical lymphoma assessments for defining events and censoring of patients who had not yet progressed. At 24 months (the time of the last protocol-mandated CT scan), there remained a substantial separation between the PFS rate for brentuximab vedotin compared with placebo.

By this analysis, the median PFS for patients who received brentuximab vedotin was not reached (95% CI [-, -]) (range, 0.03+ to 49.05+) compared with 15.8 months (95% CI [8.5, -]) (range, 0.03+ to 48.36+) for patients who received placebo. As assessed by Cox regression analysis, the stratified HR was 0.50 (95% CI [0.36, 0.70]).

By Kaplan-Meier analysis, the estimated 24-month PFS rate was 65% (95% CI [57%, 72%]) for patients in the brentuximab vedotin arm versus 45% (95% CI [37%, 52%]) for patients in the placebo arm.

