11.0 ENDPOINT EVALUATION CRITERIA/MEASUREMENT OF EFFECT

11.1 Response, Clinical Endpoints and Toxicity

11.1.1 Response/Progression

HL response/progression will be evaluated using 2014 Lugano Classification (see [Table 11.1](#)) [53, 54]. Participants who meet the definition of progressive disease per Lugano Classification should be evaluated using the LYRIC criteria (see [Appendix H](#)).

PET-CT or diagnostic quality CT of the neck, chest, abdomen, and pelvis (N/C/A/P) with IV contrast will be performed at baseline and the pre-specified time points in the study calendar. PET and CT may be co-acquired or acquired separately. Additional necessary restaging studies including dedicated CT scans, MRI, or bone marrow biopsies, are permitted at the investigator's discretion. Although diagnostic quality CT is acceptable, PET-CT is the preferred disease assessment method throughout the study, particularly for patients not in CR. Since 18-month PFS is the primary endpoint, every effort should be made to perform PET-CT at the "18-month from start of treatment" time point (particularly if the patient never achieved CR after ASCT), but if not possible, diagnostic quality CT will be acceptable. PET-CT and CT results will be read by a radiologist at each study site and investigator response based on radiology reading will be performed.

For patients with progression of disease on imaging, it is strongly recommended that a confirmatory biopsy be obtained whenever possible. Note that an FDG-negative PET scan will only be considered complete remission in patients whose tumor was FDG-avid at baseline.

A disc copy of the study-required images, including post-salvage/pre-ASCT PET scan should be sent to the Study PI upon request. Per institutional practices, the images should be de-identified (coded) and the disc should be labeled with Subject ID, COH Protocol # and institution name.

Table 11.1 2014 Lugano Classification Response Criteria

Response	Site	CT-Based Response	PET-CT Based Response

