15.6 Quality Assurance

The City of Hope Clinical Research Information Support will provide quality assurance.

An additional level of quality assurance of the study-required images will be performed by the Study PI (see [Section 11.1.1](#) for details).

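### Does a 65% null taken from AETHERA's independent review undermine a primary endpoint read by the sites?

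*Combined protocol and SAP*

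**What the plan says.** Section 12.3.1, repeated in the synopsis, gives the null and its source: "18-month PFS rate in patients with relapsed/refractory HL who undergo ASCT followed by BV consolidation is approximately 65% (from the independent assessment data"). Section 12.3.2 uses it as the test value: "the observed 18-month PFS will be compared to the baseline of 65% by one-sided exact test of binomial proportion". If there is censoring before 18 months, the Kaplan-Meier estimate with its Greenwood standard error is tested against the same 65%. The decision rule is 45 or more successes in 59. Table 12.3.1 gives the probability of meeting it at true rates of 65%, 70%, 75% and 80%.

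Section 11.1.1 says who decides progression here: "PET-CT and CT results will be read by a radiologist at each study site and investigator response based on radiology reading will be performed". Section 15.6 adds one check: "An additional level of quality assurance of the study-required images will be performed by the Study PI". No independent endpoint review is described.

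Section 2.3.2 reports AETHERA both ways at 24 months. By independent review, PFS was 63% on brentuximab vedotin (BV), with a 95% CI of 55% to 70%, and 51% on placebo. By investigator, "the estimated 24-month PFS rate was 65% (95% CI [57%, 72%]) for patients in the brentuximab vedotin arm". The placebo figure on that reading was 45%, with a 95% CI of 37% to 52%. The section presents the investigator result as a further analysis planned in advance: "analysis per investigator assessment was performed that included clinical lymphoma assessments for defining events and censoring". AETHERA's investigator-assessed rate at 18 months does not appear in the documents.

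**The concern.** In a single-arm trial the benchmark stands in for the control group, so it should measure PFS in the same way as the trial does. Here the benchmark comes from an independent reading and the endpoint from site readings, and the plan gives no reason. In AETHERA's BV arm the investigator rate was the higher of the two at 24 months (65% against 63%). PFS cannot rise with time, so the investigator rate at 18 months is at least about 65% and may well be higher. If the same-reader rate for BV alone were above 65%, the 45/59 rule would have a larger false-positive rate than the stated 0.044. A bare 45/59 could then be called promising without excluding what BV alone achieves under the same kind of reading.

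**Working it through.** **Inputs.** n = 59, cut-off 45, null 65%, alternative 80%, one-sided 5% (Section 12.3.1). AETHERA BV arm at 24 months: 63% independent, 65% investigator with CI 57% to 72% (Section 2.3.2).

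**1. The plan's own figures.** The rule's success probability is P(X ≥ 45 | p) = Σ (k = 45 to 59) C(59, k) p^k (1 − p)^(59 − k). At p = 0.65, 0.70, 0.75 and 0.80 this gives 0.0436, 0.1825, 0.4801 and 0.8124. Table 12.3.1 has 0.044, 0.18, 0.48 and 0.81, so all four reproduce. A cut-off of 44 would give 0.0775 at 65%, so 45 is the smallest cut-off with error at or below 5%.

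**2. What the documents imply for the investigator rate at 18 months.** The only firm statement is a floor: 65% at 24 months, or 64.5% if that figure was rounded to a whole number. Two rough extrapolations go further:
- adding the 24-month gap between readers to the stated 18-month rate: 65 + (65 − 63) = 67%;
- scaling by the ratio of the two readings: 65 × 65/63 = 67.1%.

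Both are assumptions built on rounded figures. A constant-hazard back-projection would give 0.65^0.75 = 72.4%. The same projection applied to the independent reading gives 0.63^0.75 = 70.7%, whereas the plan states about 65%. That model does not fit the documents' own pair of figures and is set aside.

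**3. Error of the 45/59 rule at other BV-alone rates (same formula).**

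| BV-alone rate | P(X ≥ 45 of 59) | Status of the rate |
|---|---|---|
| 64.5% | 0.037 | floor, allowing for rounding |
| 65% | 0.044 | the plan's null |
| 65.4% | 0.050 | point where 5% is reached |
| 66% | 0.060 | assumed |
| 67% | 0.082 | assumed |
| 68% | 0.109 | assumed |
| 70% | 0.183 | in Table 12.3.1 (0.18) |

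**4. Which results would be read differently.** The one-sided 95% exact lower bound is the p that solves P(X ≥ x | p) = 0.05. It is 65.4% for 45/59, 67.3% for 46/59 and 69.1% for 47/59. For a benchmark above 65.4% and up to 67.3%, 45/59 is the only passing result that fails to exclude the benchmark. Under a true rate of 80% the chance of exactly 45 is 0.8124 − 0.7175 = 0.095. Under 65% it is 0.0436 − 0.0226 = 0.021.

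**5. Scale against other uncertainty.** Over the investigator CI of 57% to 72%, the error of the same rule runs from 0.002 to 0.284. Sampling error in the benchmark is therefore larger than the assessor effect of about two points.

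**6. Cost of a stricter rule.** Holding the error at 5% against a 67% null means 46/59, and power at 80% falls from 0.81 to 0.72. Against 68% it means 47/59 and power 0.60. Keeping at least 80% power against 67% needs 73 evaluable patients (cut-off 56, error 0.0475, power 0.804), above the maximum accrual of 65.

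**The case for a change.** The best argument for acting is that the documents carry both AETHERA readings, the plan's parenthesis shows that the type of reading was noticed, and no reason is given for the choice. The null sits at the floor of the same-reader estimate, and the rule has little slack because 5% is passed at 65.4%. The trial is open-label, and reader judgement enters the endpoint again through the LYRIC provision in Section 11.1.2, under which some Lugano progressions are not counted. Table 12.3.1 has no column between 65% and 70% and labels its entries as chances of success. A modest request would be to keep 45/59 and add a second comparison with the investigator-assessed rate.

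The facts in this argument stand, and so does its direction on the BV-arm figures. The inference that the investigator rate is the right benchmark is weaker. AETHERA's investigator analysis brought clinical lymphoma assessments into events and censoring, while here the investigator's response rests on the radiology reading, with LYRIC reclassification. Neither AETHERA analysis matches fully. The gap between readers also reverses in the placebo arm (45% investigator, 51% independent), so no stable direction of reader effect is established. Other differences, such as 8 cycles against 16, could move the BV-alone rate either way.

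A second comparison would use a figure that the documents do not contain. If it were only descriptive, the decision at 45/59 would stay the same. If the word promising depended on it, it would act as a cut-off of 46/59 at an assumed 67%, with power 0.72. That would be a redesign rather than a clarification.

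**Conclusion.** The mismatch of readers is real and unexplained, but no change to the plan follows. The stated error of 0.044 and power of 0.81 are correct for the null that the plan declares, and the plan is open about where that null comes from and who reads the scans. An error above 5% requires an investigator-assessed 18-month rate above 65.4%. That is possible, but the documents do not show it. At an assumed 67% the error would be 0.082, inside the 0.044 to 0.18 that a reader can already take from Table 12.3.1. The label there says success, but the same probability is the error if BV alone has that rate.

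The choice between two imperfect benchmarks is a fair trade-off. A stricter one would lower power to 0.72 or exceed the accrual limit, while leaving the larger uncertainty in the benchmark where it is. The conclusion at stake is that a single-arm phase 2 regimen looks promising. At reporting, the planned Kaplan-Meier estimate and its standard error, or the binomial count, allow a lower bound to be set against any historical rate. This judgement rests on the 24-month figures in Section 2.3.2 and on the assumed 66% to 68% range. A same-reader 18-month rate well above that range would make the issue more serious, but nothing in the documents establishes one.
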